5.5 Dose modifications

5.5.1 Dose delays and reductions

Patients who experience a DLT (defined in Cycle 1 only) that resolves to Grade \leq 1 or recovers to baseline within 15 days of the start of the DLT may recommence treatment, with the agreement of the PI, Sponsor and patient. The dose should be reduced to a lower dose level. If the AE has not resolved to Grade \leq 1 or recovered to baseline within 15 days, the patient will be taken off-study. If the patient experiences a DLT at this reduced dose, either the same or different toxicity, there will be no further dose reductions and the patient will be withdrawn from the study.

Haematological toxicities

- Patients who experience a ≥Grade 3 haematological toxicity will have the subsequent doses omitted during that cycle until the toxicity resolves to <Grade 3. On resolution to <Grade 3, treatment can recommence at the same dose level during that cycle.
- If a clinically significant Grade 2 toxicity related to BT1718 (probably or highly probably) is still present when a patient is due to start the next cycle, that cycle should be delayed up to 14 days until the toxicity resolves to ≤Grade 1.
- The first time a dose is omitted or delayed, it may be given at the same dose the next time. However, if there is a subsequent need to omit or delay again, the dose should be reduced to a lower dose level (unless, in exceptional circumstances, the PI, Sponsor and patient agree that further dose omissions/delays are appropriate and provide effective control of toxicity).
- If toxicity remains clinically significant and does not recover to <Grade 2 within 15 days, the patient will be taken off-study.
- Only one dose reduction will be allowed per patient unless, in exceptional circumstances, the PI, Sponsor and patient agree that further treatment is appropriate and that a dose reduction is expected to provide effective control of toxicity.

Non-haematological toxicities:

Grade 2

- Patients who experience a clinically significant Grade 2 non-haematological toxicity related to BT1718 (probably or highly probably), that does not respond (<7 days) to supportive clinical management, will omit subsequent doses during that cycle until the toxicity resolves to <Grade 1 or baseline.
- If a clinically significant Grade 2 BT1718-related toxicity is still present when a patient is due to start the next cycle, that cycle should be delayed up to 14 days until the toxicity resolves to ≤Grade 1 or baseline.

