- The first time a dose is omitted or delayed, it may be given at the same dose when recommencing. However, if there is a subsequent need to omit or delay again, the dose should be reduced to a lower dose level (unless, in exceptional circumstance, the PI, Sponsor and patient agree that further dose omissions/delays are appropriate and provide effective control of toxicity).
- If toxicity remains clinically significant and does not recover to ≤Grade 1 or baseline within 15 days, the patient will be taken off-study.

• Only one dose reduction will be allowed per patient, unless, in exceptional circumstances, the PI, Sponsor and patient agree that further treatment is appropriate and that a dose reduction is expected to provide effective control of toxicity.

Grade 3

- Patients who experience a Grade 3 non-haematological toxicity that does not rapidly respond (<3 days) to supportive clinical management, will omit subsequent doses during that cycle until the toxicity resolves to ≤Grade 1 or baseline (or non clinically significant Grade 2).
- If clinically significant ≥Grade 2 BT1718-related toxicity is still present when a patient is due to start the next cycle, that cycle should be delayed up to 14 days until the toxicity resolves to ≤Grade 1 or baseline.
- When patients recommence treatment after a Grade 3 non-haematological toxicity, the dose should be reduced to a lower dose level. If toxicity does not recover to ≤Grade 1 or baseline within 15 days, the patient will be taken off-study.
- Only one dose reduction will be allowed per patient, unless, in exceptional circumstances, the PI, Sponsor and patient agree that further treatment is appropriate and that a dose reduction is expected to provide effective control of toxicity.

Grade 4

• Patients who experience a Grade 4 non-haematological toxicity, or liver enzyme changes consistent with Hy's Law (bilirubin >2x ULN and ALT/AST >3x ULN, with no explanation other than drug), will cease further treatment and be taken off-study once accuracy of testing is confirmed.

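### Section 5.5.1 puts haematological Cycle 1 DLTs under two different re-dosing rules and does not say which one governs (minor safety and consistency fix for Phase IIa)

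*Protocol*

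**What the plan says.** Section 5.5.1 opens with a paragraph on any DLT, defined for Cycle 1 only. If the event settles to Grade 1 or less, or to baseline, within 15 days of its start, the patient "may recommence treatment, with the agreement of the PI, Sponsor and patient. The dose should be reduced to a lower dose level". If it does not settle in that time, the patient comes off study.

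Bullets by type and grade of toxicity follow. The first haematological bullet covers any haematological toxicity of Grade 3 or worse: doses are omitted until it is below Grade 3, after which "treatment can recommence at the same dose level during that cycle". The third adds: "The first time a dose is omitted or delayed, it may be given at the same dose the next time". The PI, Sponsor and patient appear in these bullets only for exceptional further omissions, delays or reductions.

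For Grade 4 non-haematological toxicity, or liver changes meeting Hy's Law, patients "will cease further treatment and be taken off-study once accuracy of testing is confirmed".

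Section 3.3 lists the DLT criteria. Several are haematological: prolonged Grade 4 neutropenia, febrile neutropenia, infection with Grade 3 or 4 neutropenia, and Grade 4 thrombocytopenia that lasts, bleeds or needs transfusion.

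**The concern.** A haematological DLT meets the entry condition of both the DLT paragraph and the haematological bullets. They differ on the recovery needed, the dose, the timing and who must agree. The bullets are not limited to events other than DLTs, and no sentence gives an order of precedence.

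What is at stake is patient safety and equal handling across sites. One site could hold treatment, seek Sponsor agreement and reduce the dose. Another, with the same event, could give the full dose again in the same cycle while the count is still at Grade 2. Section 5.5.1 is not marked as completed, and Section 5.4.4 expects that DLTs may occur in the expansion phase, so the question is live for Phase IIa.

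**Working it through.** No sample size, power or error figure bears on this point. The check compares the rules with each other and with the dosing days.

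**Step 1: the two rules for a haematological Cycle 1 DLT.**

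| | DLT paragraph | Haematological bullets |
|---|---|---|
| Recovery before restart | Grade 1 or less, or baseline, within 15 days of onset | Below Grade 3 (Grade 2 is enough) within the cycle |
| Dose | Lower level | Same level |
| Agreement | PI, Sponsor and patient | None named for a first restart |

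At the start of the next cycle the gap is narrower. The bullets then require a clinically significant related Grade 2 toxicity to resolve to Grade 1 or less, and they have their own 15-day limit. The main difference left there is the dose level.

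**Step 2: which DLT criteria overlap.** Section 3.3 has eight criteria. Three fall outright under both rules: prolonged Grade 4 neutropenia, febrile neutropenia and qualifying Grade 4 thrombocytopenia. Neutropenic infection counts only when the infection itself is below Grade 3. A Grade 3 infection already calls for a lower dose, and a Grade 4 infection for stopping, under the non-haematological bullets.

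**Step 3: whether a same-cycle restart can be reached.** Section 5.2.3 refers Phase IIa to the once-weekly schedule in Section 5.2.2: Days 1, 8 and 15, each within 1 day. The last in-cycle dose is therefore no later than 15 + 1 = Day 16.

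- Grade 4 neutropenia is a DLT at 7 days: latest onset 16 − 7 = Day 9.
- Grade 4 thrombocytopenia is a DLT by duration at 5 days: latest onset 16 − 5 = Day 11.
- At those latest onsets the count must fall from Grade 4 to below Grade 3 almost at once, so both windows are narrow.
- Febrile neutropenia, and Grade 4 thrombocytopenia with bleeding or transfusion, have no minimum duration. These are the main cases.

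**Step 4: example.** Febrile neutropenia starts on Day 9, after the Day 8 dose, and neutrophils are at Grade 2 on Day 15.

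- Haematological bullet: full dose on Day 15, with no dose missed.
- DLT paragraph: no dose on Day 15. The recovery limit is 9 + 15 = Day 24. If recovery to Grade 1 or baseline comes after Day 16 but by Day 24, and all parties agree, a lower dose follows on Cycle 2 Day 1, which is 28 + 1 = Day 29.
- Difference: 29 − 15 = 14 days, and one dose level.

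**Step 5: non-haematological DLTs.** After a Grade 3 event both texts require a lower dose and set a 15-day limit, so the dose does not conflict. After a Grade 4 event the DLT paragraph allows a conditional restart while the Grade 4 bullet requires stopping.

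**Step 6: other sections.** Section 9.2.2 has DLTs reported to the Sponsor within 24 hours. Section 5.3.4 provides for emails on actions where needed. Section 7.2.2 has the investigator review laboratory results before dosing. None of these sets precedence or makes the restart wait for agreement.

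**The case against.** The strongest reply is that nothing here is a true contradiction. The DLT paragraph comes first, names one special class of event and sets its conditions. Its provision for a further DLT at the reduced dose takes for granted that the reduction has been made. The looser bullets only permit, so a site that follows the stricter rule obeys both texts. For Grade 4 non-haematological events a prohibition overrides a permission, and a restart would need Sponsor agreement anyway. Sponsor notification and continual tolerability monitoring (Section 5.4.4) make an unseen restart unlikely.

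Most of this stands, and it is why the point is minor. It does not remove the point. That the special rule wins is an inference, and applied throughout it would allow a restart after a Grade 4 non-haematological DLT, against the Grade 4 bullet. The principle that works in every case is that the stricter text applies, and the protocol does not state it. Notification is also not a hold on dosing.

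A reader might infer that the protocol endorses full-dose re-treatment after DLTs in general, that DLT counts or the recommended dose are compromised, or that all of the up to 70 expected Phase IIa patients are exposed. The documents support none of these. A DLT is counted when it occurs, whatever dose follows. Phase I has completed. The figure of 70 is an enrolment ceiling, and only a patient with one of a few Cycle 1 events is affected.

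**Conclusion.** The point holds as a minor patient-safety and consistency gap. Section 5.5.1 places haematological Cycle 1 DLTs under two rules with different recovery, dose and agreement requirements and does not say which prevails. The practical reach is mainly febrile neutropenia, or Grade 4 thrombocytopenia with bleeding or transfusion, recovering by about Day 15 or 16. The Grade 4 non-haematological mismatch is real in wording but low in risk. Endpoints, DLT counts and error rates are unaffected.

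This assumes that febrile neutropenia is handled as a haematological toxicity and that Phase IIa patients still enter Cycle 1 under this text. The protocol gives no DLT rate by type, so no frequency is estimated.

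**What to change.** Add to Section 5.5.1:

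*Any event that meets the DLT definition in Section 3.3 is managed under the first paragraph of this section; the bullets that allow the same dose or an earlier restart apply only to toxicities that are not DLTs. Where rules overlap, the stricter applies. Grade 4 non-haematological toxicity or Hy's Law changes, once the test result is confirmed as accurate, mean permanent discontinuation whether or not the event is a DLT.*

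The confirmation condition is already in the Grade 4 bullet and should be kept, so that a spurious laboratory value does not end treatment. The cost is one short amendment to one section, with no added patients, visits or procedures. The downside is that a few patients with haematological DLTs will receive a lower or later dose than the bullets would have allowed.

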5.7 Concomitant medication and treatment

Concomitant medication may be given as medically indicated. This includes symptomatic clinical management of BT1718 related or unrelated AEs. Vaccinations, including COVID-19 vaccines are permitted. Some vaccinations may be subject to specific Sponsor risk assessment. Details (including name and start and stop dates of the concomitant medication given) must be recorded in the patient's medical records and details entered into the electronic case report form (eCRF).

Palliative radiotherapy may be given concomitantly for the control of bone pain or other symptoms. These irradiated lesions will not be evaluable for response.

The patient must not receive other anti-cancer therapy or investigational drugs while on the trial.

As in Section 5.5 above, dosing with BT1718 may also be delayed up to 15 days if required to manage toxicity, without a patient needing to be withdrawn from study.

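### Section 5.5.1: after a Grade 3 non-haematological toxicity, a residual non clinically significant Grade 2 permits further dosing but requires withdrawal at 15 days

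*Protocol*

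**What the plan says.** Protocol Section 5.5.1 gives separate rules for non-haematological toxicity by grade. Three consecutive bullets of the Grade 3 block bear on the same patient:

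- **In-cycle dosing.** A patient whose event does not settle quickly with supportive care "will omit subsequent doses during that cycle until the toxicity resolves to ≤Grade 1 or baseline (or non clinically significant Grade 2").
- **Next cycle.** "If clinically significant ≥Grade 2 BT1718-related toxicity is still present when a patient is due to start the next cycle", the start is put back by up to 14 days.
- **Restart and withdrawal.** Treatment resumes at a lower dose level, and "If toxicity does not recover to ≤Grade 1 or baseline within 15 days, the patient will be taken off-study".

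The neighbouring off-study sentences are conditional. The Grade 2 block has "If toxicity remains clinically significant and does not recover to ≤Grade 1 or baseline within 15 days, the patient will be taken off-study", and the haematological block has "If toxicity remains clinically significant and does not recover to <Grade 2 within 15 days, the patient will be taken off-study". Section 5.6 lets a benefiting patient continue, with Sponsor and Chief Investigator agreement, if there is no related event that is both Grade 2 or above and clinically significant.

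On timing, the DLT paragraph of 5.5.1 counts recovery "within 15 days of the start of the DLT". The grade blocks and the haematological block also use 15 days but name no starting day. Section 5.7, referring back to 5.5, says "dosing with BT1718 may also be delayed up to 15 days if required to manage toxicity".

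**The concern.** Two of the three Grade 3 bullets treat a Grade 2 that is not clinically significant as acceptable for further dosing. The third makes the same state a reason for compulsory withdrawal once 15 days have passed. Investigators at two sites could each follow the text and record opposite outcomes, one continuing the patient at a reduced dose and the other reporting a toxicity withdrawal.

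At stake is how tolerability is described in Phase IIa. Section 13.1 gives further characterisation of the tolerability of the RP2D as a purpose of each expansion cohort, and Section 13.2 reports dose modifications, delays and duration of therapy. Those summaries would partly reflect which sentence was applied.

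**Working it through.** The plan gives no figure to reproduce. The check applies each rule to every residual state and then counts days.

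**Step 1: the rules by residual state.** Take a patient 15 days after a non-haematological toxicity, with any residual grade above baseline. A residual Grade 3 is taken to be clinically significant. The first three rule columns come from the Grade 3 block of 5.5.1 and the last from the Grade 2 block.

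| Residual state | In-cycle dosing allowed (Grade 3 block) | Next cycle may start (Grade 3 block) | Off-study (Grade 3 block) | Off-study (Grade 2 block) |
|---|---|---|---|---|
| Grade 0 | yes | yes | no | no |
| Grade 1 | yes | yes | no | no |
| Grade 2, not clinically significant | **yes** | **yes** | **yes** | **no** |
| Grade 2, clinically significant | no | no | yes | yes |
| Grade 3 | no | no | yes | yes |

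The Grade 3 bullets contradict each other in one of the five states. In that state the Grade 2 block keeps the patient and the Grade 3 block removes the patient. Section 5.6 also points towards continuation there. The exceptional-circumstances clauses in 5.5.1 do not resolve it: they cover repeat omissions or delays and further dose reductions, not the off-study sentence.

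**Step 2: which events are affected.** In Cycle 1, a probably or highly probably related Grade 3 non-marrow toxicity is generally a DLT under Section 3.3, and the DLT paragraph of 5.5.1 then governs. That paragraph requires Grade 1 or below, or baseline, and states its clock. The conflict therefore concerns events from Cycle 2 onward and Cycle 1 events that are not DLTs, such as Grade 3 nausea, which Section 3.3 excludes.

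Illustration, Cycle 2, once weekly: a Grade 3 event starts on Day 3 and settles to a non clinically significant Grade 2 by Day 8. The first bullet allows dosing on Days 8 and 15. If the limit runs from onset, the third bullet removes the patient on Day 3 + 15 = Day 18.

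**Step 3: the clock.** In a 28-day cycle the next cycle is due on Day 29, and the 14-day delay in 5.5.1 runs to Day 29 + 14 = Day 43.

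| Assumed start of the 15-day limit | Limit reached | Distance from Day 43 |
|---|---|---|
| Onset on Day 9 | 9 + 15 = Day 24 | 19 days earlier |
| Onset on Day 16 | 16 + 15 = Day 31 | 12 days earlier |
| Onset on Day 28 | 28 + 15 = Day 43 | 0 days |
| Next-cycle due date (Day 29) | 29 + 15 = Day 44 | 1 day later |

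The documents do not say which row applies outside a DLT. Sections 5.5.1 and 5.7 themselves differ by 15 − 14 = 1 day.

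**Step 4: scale.** With about 16 evaluable patients per cohort, one patient is 1/16 = 6.25 percentage points. How many patients will reach this state cannot be derived from the documents.

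**The case against.** The strongest reply is that the third bullet covers only patients who have not restarted, so the bullets apply in sequence. That reading is possible, but the text does not limit the sentence in that way. It is also true that the Sponsor has the final say on continuation under Section 5.6. That may reduce variation between sites, but it leaves the written rules in conflict.

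A reader might draw four stronger conclusions, none of which the documents support.

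- **That the milder event is handled more strictly overall.** The Grade 2 block does say "will omit subsequent doses during that cycle until the toxicity resolves to <Grade 1 or baseline", a tighter in-cycle threshold than for Grade 3. This holds for in-cycle restart only; for withdrawal the order reverses. A Grade 3 restart is at a reduced dose, while a first Grade 2 omission may resume at the same dose, so the two thresholds can be a coherent pair. The strict sign before Grade 1 may also be a lost ≤ in the text read from PDF, since the later bullets of that block use ≤.
- **That withdrawal dates differ by 12 or 19 days.** Those gaps require the limit to run from onset. Counted from the due date, the gap is one day. The 14 days are also a ceiling, so an earlier off-study rule can be obeyed alongside it.
- **That 14 against 15 days is a serious conflict.** It equals the ±1 day dosing window, and the 15 days in 5.7 match the off-study limit in 5.5.1.
- **That response evaluability is affected.** The patient in the illustration has had Days 1, 8 and 15 before Day 18, which is a full cycle. The exposure criterion in Section 3.5.1 is already met.

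The expansion-phase primary endpoint in Section 3.1.1 is adverse event frequency, causality and grade, not discontinuation. This limits the consequence.

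**Conclusion.** The contradiction is real and narrow. For events outside the Cycle 1 DLT paragraph, a patient left with a non clinically significant Grade 2 above baseline after a Grade 3 non-haematological toxicity may be dosed under two bullets and must be withdrawn under the third. The withdrawal sentence also departs from the matching sentences in the Grade 2 and haematological blocks and from the continuation standard in Section 5.6. This is an error in what is written, not detail that could wait for an analysis plan.

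The effect falls on toxicity withdrawals and treatment duration in the expansion cohorts. Its frequency is unknown. The missing start of the 15-day limit is a secondary point: its effect ranges from no difference to weeks, depending on an assumption the documents leave open. The one-day mismatch with 5.7 is minor.

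**What to change.** The sponsor and Chief Investigator should:

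- reconcile the three Grade 3 bullets, so that each residual state has one instruction for in-cycle dosing, next-cycle start and withdrawal;
- reconcile them with the Grade 2 and haematological off-study sentences and with Section 5.6;
- state the day from which the 15-day limit runs in each block;
- align the delay limits in 5.5.1 and 5.7, or state that they measure different things;
- check the inequality sign in the Grade 2 in-cycle bullet against the source file.

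Which threshold or limit applies is a clinical decision for them, and none is proposed here. The cost is wording in 5.5.1, 5.6 and 5.7 within one amendment, with no added patients or procedures.

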5.6 Duration of treatment

Treatment should continue unless (a) the patient asks to be withdrawn, (b) there is evidence of disease progression, (c) the patient is experiencing unacceptable toxicity or (d) the Investigator feels the patient should be withdrawn for any other reason. Other reasons are listed in Section 11.

If the Sponsor and CI agree that a patient is benefiting from treatment with BT1718 (i.e. has stable or responding disease as measured by RECIST V1.1) and is not experiencing any clinically significant Grade 2 or greater BT1718-related AEs, the patient may continue with treatment until disease progression (depending on the availability of BT1718), after which the patient will be withdrawn from the trial. Follow up information should be collected as described in the protocol (see Section 7.4).

The Sponsor will review a full toxicity and efficacy profile including radiological data to confirm the reported objective response for that patient when considering whether the patient should continue to receive treatment. If the Sponsor decides not to allow the patient to continue treatment based on the information provided or on other information received, or for any other reason, then the Sponsor's decision is final.

5.6.1 Replacement of patients

5.6.1.1 Phase I, dose escalation phase (Stage 1 and Stage 2)

Patients will be replaced by another patient treated at the same dose level during the dose escalation phase if they receive less than 75% of planned dose exposure of BT1718 during the first cycle (28 day DLT period) for reasons other than BT1718-related (probably or highly probably) toxicity. For single-patient cohorts, patients may be replaced if they do not receive all their planned doses.

Phase I of the trial has completed.

